**NOTES:**

- If the treatment stop date is missing and the treatment start date is non-missing, and Date > Treatment Start Date, then the assessment will be considered to be On-Treatment

#### 14.4.1.2. Study Phases for CV Endpoint Data

Study Phase	Definition
Pre-Treatment	Date < Treatment Start Date
On-Treatment	Treatment Start Date $\leq$ Date $\leq$ Last Non-Zero Dose Date + 28 days
Post-Treatment	Date > Last Non-Zero Dose Date + 28 days
Post-Randomization	Randomization Date $\leq$ Date

**NOTES:**

- If the last non-zero dose date is missing and the treatment start date is non-missing, and Date  $\geq$  Treatment Start Date, then the assessment will be considered to be On-Treatment
- Study phase definitions use the imputed CV endpoint date

#### 14.4.1.3. Study Phases for BP, Lipid Parameters, Clinical Chemistry, Hematology, Other Laboratory Tests, Hepatobiliary (Liver), ECG and Vital Signs Data

Study Phase	Definition
Pre-Treatment	Date $\leq$ Treatment Start Date
On-Treatment	Treatment Start Date < Date $\leq$ Last Non-Zero Dose Date + 1 day
Post-Treatment	Date > Last Non-Zero Dose Date + 1 day
Post-Randomization	Randomization Date < Date

**NOTES:**

- If the last non-zero dose date is missing and the treatment start date is non-missing, and Date > Treatment Start Date, then the assessment will be considered to be On-Treatment
- Post-dialysis BP measured on treatment start date is considered on-treatment

CONFIDENTIAL

204837

**14.4.1.4. Study Phase for AE Data**

All AEs (non-serious AEs and serious AEs) will be collected and recorded on the eCRF from the start of treatment until the follow-up visit at the time points specified in the SoA from Section 14.2. Serious AEs assessed as related to study participation (e.g., study treatment, protocol-mandated procedures, invasive tests, or change in existing therapy) or related to a GSK product will be recorded on the eCRF from the time a participant consents to participate in the study up to and including any follow-up contact. AE of worsening of an on-going event will be counted once in a particular study phase.

Study Phase	Definition
Pre-treatment	
 
For subjects with a non-missing screen failure date, if AE onset is on or before the screen failure date: AE Start Date <math>\leq</math> Screen Failure Date
 
For randomized subjects with a missing treatment start date, all AEs are considered pre-treatment
 
For randomized subjects with a non-missing treatment start date, if AE onset date is before treatment start date: AE Start Date <math><</math> Treatment Start Date
 

Post-randomization	
If AE onset date or AE worsening date is on or after the randomization date  Randomization date <math>\leq</math> AE Start Date  Randomization date <math>\leq</math> AE Worsening Date  AE worsening during post-randomization will be defined relative to the maximum intensity of AE prior to randomization date.
 
AE worsening date is the first date in the post-randomization period, when AE intensity increased relative to the maximum intensity of the AE prior to randomization date.

Treatment emergent	
If AE onset date or AE worsening date is on or after treatment start date & on or before the last non-zero dose date plus 1 day.  Treatment Start Date <math>\leq</math> AE Start Date <math>\leq</math> Last Non-Zero Dose Date + 1 day  Treatment Start Date <math>\leq</math> AE Worsening Date <math>\leq</math> Last Non-Zero Dose Date + 1 day  AE worsening during treatment emergent period will be defined relative to the maximum intensity of AE prior to study treatment start date.
 
AE worsening date is the first date in the treatment emergent period, when AE intensity increased relative to the maximum intensity of the AE prior to study treatment start date.

Follow-up	
If AE onset date or AE worsening date is after the last non-zero dose date plus 1 day.  AE Start Date <math>></math> Last Non-Zero Dose Date + 1 day  AE Worsening Date <math>></math> Last Non-Zero Dose Date + 1 day  AE worsening during follow-up will be defined relative to the maximum intensity of AE prior to study treatment start date.
 
AE worsening date is the first date in the follow-up period, when AE intensity increased relative to the maximum intensity of the AE prior to study treatment start date.

Onset /Worsening Time Since 1 st Dose (Days)	
If Treatment Start Date <math>></math> AE Onset Date: AE Onset Date - Treatment Start Date  If Treatment Start Date <math>\leq</math> AE Onset Date: AE Onset Date - Treatment Start Date +1  If Treatment Start Date <math>></math> AE Worsening Date: AE Worsening Date - Treatment Start Date

CONFIDENTIAL

204837

Study Phase	Definition
	If Treatment Start Date $\leq$ AE Worsening Date: AE Worsening Date - Treatment Start Date + 1 Missing otherwise.
Onset/Worsening Time Since Last Dose (Days)	If Last Non-Zero Dose Date $\leq$ AE onset date: AE onset date – last non-zero dose date + 1 If Last Non-Zero Dose Date $>$ AE onset date: AE onset date – last non-zero dose date If Last Non-Zero Dose Date $\leq$ AE worsening date: AE worsening date – last non-zero dose date + 1 If Last Non-Zero Dose Date $>$ AE worsening date: AE worsening date – last non-zero dose date Missing otherwise.
Duration (Days)	AE Resolution Date – AE Onset Date/AE Worsening Date + 1
Drug-related	If relationship is marked 'YES' on eCRF or if the value is missing.

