2. SCHEDULE OF ACTIVITIES (SOA)

Table 1 Schedule of Activities

Procedure Visit window of ± 3 days for Weeks 2 to 8, and ± 1 week for all other visits. All visit timings are relative to Day 1. All assessments will be performed pre-dialysis unless otherwise specified.	Screening (Week -4)	Treatment Period: Day 1 through Week 52					Follow-up Visit (4 to 6 weeks after last dose)
		Day 1 ¹	Full Study Visit Week 4, 16, 28, 40	Abbreviated Study Visit Week 2, 6, 8, 12, 20, 24, 32, 36, 44, 48	Week 52	Unscheduled ²	
Informed consent	X						
IRT system transaction ³	X	X	X	X	X	X	X
Inclusion and exclusion criteria	X	X					
Randomization ⁴		X					
Study Treatment Dispensing ^{5,6}		X	X	X ⁷		X ⁷	
Study Treatment Compliance ⁶			X	X ⁷	X	X ⁷	
Participant reminder to report changes in health ⁸		X					
Medical history (including past and current medical conditions, hospitalization and transfusion) ⁹	X						
Demography, height	X						
Weight (pre- and post-dialysis) and EDW ¹⁰	X	X	X	X	X	X	X
SBP/DBP, HR (pre- and post-dialysis)	X	X (triplicate)	X	X	X (triplicate)	X	X
Kt/Vurea ¹¹		X	X		X		
12-lead ECG ¹²	X				X		
Ultrasound of kidneys and adrenal glands ¹³	X						
Estradiol and FSH (females only, if required) ¹⁴	X						
Serum pregnancy test (WOCBP only) ^{15,16}	X	X	X		X		X
HemoCue Hgb	X	X	X	X	X	X	
Hematology ¹⁷	X	X	X	X (Hgb only)	X	X	X
Clinical chemistry ¹⁷	X	X	X		X	X	X
Ferritin, total iron and UIBC ¹⁷	X	X	X		X		X

Procedure Visit window of ± 3 days for Weeks 2 to 8, and ± 1 week for all other visits. All visit timings are relative to Day 1. All assessments will be performed pre-dialysis unless otherwise specified.	Screening (Week -4)	Treatment Period: Day 1 through Week 52					Follow-up Visit (4 to 6 weeks after last dose)
		Day 1 ¹	Full Study Visit Week 4, 16, 28, 40	Abbreviated Study Visit Week 2, 6, 8, 12, 20, 24, 32, 36, 44, 48	Week 52	Unscheduled ²	
Lipids (non-fasting) ¹⁷		X	X		X		
iPTH, hsCRP, HbA1c ^{17, 18}		X	Wk 28		X		
Hepcidin ^{17, 19}		X	Wk 4, 16, 28		X		
PD: EPO, VEGF ¹⁷		X	X (once from Wk 28 to Wk 52) ²⁰				
PK		X	X (once from Wk 8 to Wk 52) ²¹				
Stored samples for biomarkers ²²		X	Wk 28		X		
Genetic sample ²³		X					
Patient Global Impression of Severity (PGI-S) ²⁴		X	Wk 28	Wk 8, 12	X		
Patient Global Impression of Change (PGI-C) ²⁴			Wk 28	Wk 8, 12	X		
Non-serious AEs, SAEs, AEs of Special Interest, clinical events	X ²⁵	X	X	X	X	X	X
Concomitant medication review	X	X	X	X	X	X	X
Iron therapy, transfusions, rescue medications ^{26, 27}	X	X	X	X	X	X	X

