5. STUDY DESIGN

5.1. Overall Design

- This is a randomized, double-blind, active-controlled, parallel-group, multi-center study in hemodialysis-dependent participants, including combination methods such as hemodiafiltration or hemofiltration with HD, who have anemia of CKD and are currently treated with rhEPO or its analogs.
- This study includes a 4-week Screening Period, a 52-week Treatment Period and a Follow-up Period (Figure 1).
- The 52-week Treatment Period consists of:
 - The Stabilization Period (SP), defined as the period from Day 1 to Week 28 (up to but excluding the Week 28 visit), during which study treatment will be dose-titrated to achieve and maintain Hgb in the target range.
 - The Evaluation Period (EP), defined as the period from Week 28 to Week 52, to assess long-term efficacy and safety. The study treatment may be dose-titrated, if needed, during this period to achieve or maintain Hgb level in the target range.

Figure 1 Study Schematic

- Each participant will remain in the study for up to 62 weeks. Participants who permanently discontinue study treatment will remain in the study.

- Randomization will be stratified by region (see [Appendix 7](#)). Following stratification, participants will be randomized 2:1 to daprodustat or epoetin alfa. Daprodustat will be administered three-times weekly and epoetin alfa will be administered once weekly or three-times weekly, depending on dose level (Section 7).
- Due to the difference in formulations between the investigational product and active control (tablets versus IV injection), and in order to maintain the study blind, each participant will receive a tablet and an IV study treatment; one will be active and one will be inactive (Section 7). Participants randomized to receive daprodustat will also receive saline IV injection. Participants randomized to receive epoetin alfa will also receive placebo tablets.
- PK samples will be collected from all study participants to enable exposure-response and exposure-safety analyses (Section 9.5).
- Adjustment of both study treatments (tablet and IV injection formulations) will follow a protocol-specified study treatment dose adjustment algorithm to achieve and maintain Hgb within the target range of 10.0 to 11.0 g/dL, inclusive (Section 7.2). Dose changes will be made programmatically by the Interactive Response Technology (IRT) system for both study treatment arms.

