7.2.2.2. Epoetin Alfa (and Saline) Titration Doses

Pre-defined dose steps of epoetin alfa are outlined in [Table 6](#). Dose adjustments of epoetin alfa will be made by increasing or decreasing the dose one step at a time, as described in the dosing algorithm ([Table 7](#)). The epoetin alfa dose steps consist of a weekly dose change between 20 to 33% for most steps, except for an increase to a weekly dose of 3000 U, which is a 50% increase, or an increase to doses of 21,000 U per week or greater, which represent increases of approximately 10 to 15%.

Participants who are receiving the highest dose of epoetin alfa (i.e., 60,000 U/week) and require a dose increase will maintain the same dose. Participants who are receiving the lowest available dose of epoetin alfa (i.e., 1500 U/week IV) and require a dose decrease will receive saline in order to maintain the blind. When a dose interruption is required by the dosing algorithm ([Table 7](#)), both epoetin alfa and placebo tablets will be interrupted in order to maintain the blind.

Participants who are randomized to epoetin alfa treatment will also receive inactive treatment for the tablet formulation (placebo tablets). When a dose adjustment is required for these participants, their placebo tablet dose will be adjusted (in addition to the epoetin alfa dose) in order to maintain the blind, such that placebo tablets matching the new corresponding daprodustat dose will be administered ([Table 5](#)).

Additional information about the delivery of the respective epoetin alfa doses is provided in the SRM.

Table 6 Number of Vials and Vial Combinations to Achieve Prescribed Epoetin Alfa or Saline Treatment

Total Weekly Dose (Units)	Dose and Frequency	Epoetin Alfa Randomized Participants ¹					Inactive (Saline) Treatment for Daprodustat Randomized Participants
		Saline ³ (1 mL)	2000 U/ 1mL	3000 U/ 1mL	4000 U/ 1mL	10000 U/ 1mL	Saline ³ (1 mL)
0	0 U once a week	1					1
1500 ⁴	1500 U once a week		0.75				0.75
2000	2000 U once a week		1				1
3000	3000 U once a week			1			1
4000	4000 U once a week		2				2
5000	5000 U once a week		1	1			2
6000	6000 U once a week		1		1		2
8000	8000 U once a week				2		2
10,000	10,000 U once a week		1		2		3
12,000	4000 U three times a week				1		1
15,000	5000 U three times a week		1	1			2
18,000	6000 U three times a week		1		1		2
21,000	7000 U three times a week			1	1		2
24,000	8000 U three times a week				2		2
27,000	9000 U three times a week		1	1	1		3

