**8.3.3. Serious and Other Significant Adverse Events**

The number and percentage of subjects and the number of occurrences of SAEs will be provided for each treatment group. These events will be summarized by treatment group, primary system organ class, and preferred term. Pre-treatment, post-randomization, treatment emergent and follow-up SAEs will be summarized separately. Treatment emergent SAE preferred terms will also be summarized by treatment group and overall frequency.

A listing of reasons for considering as a SAE will be produced for all SAEs.

The number and percentage of subjects and the number of occurrences of treatment emergent drug-related SAEs, drug-related non-SAEs, fatal SAEs, non-fatal SAEs, and drug-related fatal SAEs will be summarized by treatment group: by primary system organ class and preferred term and separately by overall frequency.

A listing of fatal SAE records and a listing of non-fatal SAE records will be provided.

The number and percentage of subjects reporting treatment emergent SAEs will be summarized by treatment group, maximum intensity, primary system organ class, and preferred term.

The number and percentage of subjects reporting treatment emergent AEs leading to discontinuation of study treatment or withdrawal from the study will be summarized by treatment group, primary system organ class, and preferred term. Treatment emergent AEs leading to discontinuation of study treatment or withdrawal from the study will also be summarized by treatment group and overall frequency.

A listing of AEs leading to discontinuation of study treatment and a listing of AEs leading to withdrawal from study will be provided.

BP events and BP-related SAEs are defined in Section [14.6.4](#).

The number and percentage of subjects with at least one on-treatment BP event will be provided for each treatment group. In addition, this summary will include the number and percentage of subjects with at least one on-treatment BP event that is considered clinically significant and the number and percentage of subjects with at least one on-treatment BP event that is considered to be symptomatic.

The number and percentage of subjects reporting at least one treatment emergent BP-related SAE will be provided for each treatment group. In addition, the number of treatment emergent BP-related SAEs will be summarized by treatment group, primary system organ class, and preferred term.

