**NOTES:**

- AEs that occur or worsen during interruptions of randomized study treatment will be classified as treatment emergent and post-randomization.
- If the last non-zero dose date is missing and the treatment start date is non-missing and the AE onset date or AE worsening date is on or after the treatment start date, then the AE will be considered to be treatment emergent.
- If AE onset date or AE worsening date is missing and AE resolution date is before the treatment start date, then the AE will be classified as Pre-treatment.
- If AE onset date or AE worsening date is missing and AE resolution date is either missing or on or after treatment start date, then the AE will be classified as treatment emergent and post-randomization.

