## 14.6. Appendix 6: Derived and Transformed Data

### 14.6.1. General

Multiple Measurements at One Time Point
 
 
• Mean of the measurements will be calculated and used in any derivation of summary statistics but if listed, all data will be presented. 
 
○ Triplicate BP and HR measurements are expected at certain time points (See Section 14.2.1)
 
 
 
• Subjects having both High and Low values for Normal Ranges at any post-baseline visits for safety parameters will be counted in both the High and Low categories of “Any visit post-baseline” row of related summary tables. This will also be applicable to relevant Potential Clinical Importance summary tables.
 

Randomization Date
 
 
• Date subject was randomized
 

Treatment Start Date
 
 
• First randomized treatment dose start date
 

Last Non-Zero Dose Date
 
 
• Date of last actual dose of active study treatment from the eCRF Study Treatment/Compliance Record Form. 
 
○ The dose steps used by the dosing algorithm described in the protocol include a dose hold or a zero dose. If subjects are assigned by the algorithm to a zero dose, they only receive placebo and saline, and do not receive active study treatment for that period. When a dose interruption is required, both active treatment and placebo/saline will be interrupted. Hence, it would be possible for a subject to complete the study, while still following the dosing algorithm, but not actually taking any active study treatment. The last non-zero dose date, then captures the latest date in the study that a subject physically took a dose of active study treatment.
 
 
 

Treatment Stop Date
 
 
• Calculated as the latest study treatment dose stop date, after excluding the records for missed dose.
 

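### The treatment-emergent window closes one day after the last active dose, so for some fatal and treatment-stopping AEs it captures fewer events on once-weekly epoetin than on daprodustat; the tables for those events have no other version

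*SAP*

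**What the plan says.** SAP section 14.4.1.4 closes the treatment-emergent period for AEs "on or before the last non-zero dose date plus 1 day"; anything later is classed as follow-up. Section 14.6.1 ties the anchor to active drug: "The last non-zero dose date, then captures the latest date in the study that a subject physically took a dose of active study treatment". Placebo tablets and saline therefore do not extend the window.

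The active-dose interval differs by arm. Protocol section 5.1 states: "Daprodustat will be administered three-times weekly and epoetin alfa will be administered once weekly or three-times weekly, depending on dose level". In Table 6 of protocol section 7.2.2.2 the highest weekly level is "10,000 U once a week" and the next step up is "4000 U three times a week", that is, 12,000 U/week. Of the 19 non-zero levels, 8 are once weekly (1500 to 10,000 U/week) and 11 are three times weekly.

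A note to section 14.4.1.4 adds: "AEs that occur or worsen during interruptions of randomized study treatment will be classified as treatment emergent and post-randomization".

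For SAEs as a whole, section 8.3.3 covers every phase: "Pre-treatment, post-randomization, treatment emergent and follow-up SAEs will be summarized separately". For fatal SAEs, and for AEs that lead to stopping treatment or leaving the study, the same section plans treatment-emergent summaries only. The display list in section 14.10.8 agrees: Tables 3.108 to 3.111, 3.114 and 3.115 are all treatment emergent, and none has a post-randomization counterpart.

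**The concern.** A one-day tail is shorter than the dosing interval in both arms, and the interval is longer on weekly epoetin. Consider an event that begins three days after the last active dose and ends dosing. On daprodustat such a gap arises only at the longest interval of the week, so most events of this kind fall nearer to a dose. On weekly epoetin the gap can reach seven days. The same event can be treatment emergent in one arm and follow-up in the other for no reason except dosing frequency.

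Fatal and treatment-stopping events are the most exposed, because the event itself is often why no further active dose was given. With equal true incidence, the affected tables could show a small excess on daprodustat that the window created.

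**Working it through.** The documents give no capture percentage, so there is no plan figure to reproduce.

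**Inputs from the documents**
- Window: the last active dose date plus one day, on calendar dates (SAP 14.4.1.4, 14.6.1).
- Daprodustat three times weekly on dialysis days, with gaps of 2, 2 and 3 days on the Monday-Wednesday-Friday pattern used as an example in protocol section 9.
- Epoetin at or below 10,000 U/week: one gap of 7 days.
- Arm sizes: 268 and 134 (protocol 10.1.1).

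**Assumptions, not in the documents**
- Onset is uniform over the week.
- No active dose is given after onset.
- The dose is given at the same time of day in both arms, at fraction h of the day (0 = start, 1 = end).

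**Capture in the affected class of event**

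The window lasts the rest of the dose day plus the next day, or 2 − h days. It never exceeds the shortest gap of 2 days, so:
- Three times weekly: a = 3(2 − h)/7
- Once weekly: b = (2 − h)/7

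| Time of dose | a | b | a/b |
|---|---|---|---|
| Start of day (h = 0) | 6/7 = 85.7% | 2/7 = 28.6% | 3.0 |
| Mid-day (h = 0.5) | 4.5/7 = 64.3% | 1.5/7 = 21.4% | 3.0 |
| End of day (h = 1) | 3/7 = 42.9% | 1/7 = 14.3% | 3.0 |

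A simulation at mid-day gave 64.1% and 21.4%. Epoetin at 12,000 U/week or more has capture a, so that ratio is 1. An event followed by an active dose is captured in both arms.

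**From the class to a whole table**

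Let t be the share of a table's eligible events that are of the affected type, and f the share of the epoetin arm dosed weekly. Neither is in the documents. If all other events are captured in both arms, the daprodustat-to-epoetin ratio at equal true incidence is

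[(1 − t) + at] / [(1 − t) + t(bf + a(1 − f))].

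With mid-day dosing:

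| t | f = 25% | f = 50% | f = 75% |
|---|---|---|---|
| 100% | 1.20 | 1.50 | 2.00 |
| 50% | 1.07 | 1.15 | 1.24 |
| 25% | 1.03 | 1.06 | 1.10 |

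**Illustration in participants** (assumed: 10% of each arm has a fatal SAE, t = f = 50%, mid-day dosing)
- Daprodustat captures 0.5 + 0.5 × 0.643 = 0.821 of events: 26.8 × 0.821 = 22.0 of 268 (8.2%).
- Epoetin captures 0.5 + 0.5 × (0.5 × 0.214 + 0.5 × 0.643) = 0.714: 13.4 × 0.714 = 9.6 of 134 (7.1%).
- At the daprodustat rate the epoetin arm would show 13.4 × 0.821 = 11.0. The shortfall is 11.0 − 9.6 = 1.4 participants.
- The shortfall equals 13.4 × t × f × (a − b). Over the range of dosing times it runs from 13.4 × 0.25 × 2/7 = 1.0 to 13.4 × 0.25 × 4/7 = 1.9.

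**The case against.** The strongest reply is that little is lost. AE analyses are descriptive (protocol 10.3.2), no confirmatory test is touched, and the bias runs against the test drug. Many outputs lie outside the window:
- deaths: survival status (Table 1.011), adjudicated all-cause mortality (3.025) and its causes (3.034);
- reasons for stopping: the outcome of AEs that led to withdrawal (1.001) and the reasons for ending treatment (1.004);
- all AEs and all SAEs in post-randomization and follow-up form (3.090, 3.091, 3.102, 3.103);
- Listings 3.006 to 3.009, whose titles carry no treatment-emergent limit.

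This stands, and it keeps the point minor. The checks remain partial, however. The SAE tables are not split by fatal outcome, adjudicated mortality is not the same as investigator-reported fatal SAEs by preferred term, Table 1.004 gives reasons rather than AE terms, and listings do not compare arms.

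A second reply is that the note on interruptions already covers these events. It may well cover an interruption that later becomes permanent. It does not cover onset inside an ordinary weekly gap, where nothing has been interrupted.

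Third, many AEs that lead to discontinuation are first observed over further doses, and those are treatment emergent in both arms. That is correct. If half are followed by another active dose, overall capture with mid-day dosing is 0.5 + 0.5 × 0.643 = 82% on daprodustat and 0.5 + 0.5 × 0.214 = 61% on once-weekly epoetin.

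**Conclusion.** The point holds as a minor one. For AEs with onset after the last active dose and no active dose afterwards, capture on once-weekly epoetin is one third of that on daprodustat: 14–29% against 43–86%, under uniform onset, 2-2-3-day gaps and a common dosing hour. The threefold ratio does not depend on that hour.

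A reader might infer more than the documents support:
- That 64% and 21% describe the trial. They are the mid-day case only, and 21% is not an epoetin-arm figure, because 11 of the 19 non-zero levels are three times weekly and the share of participants on weekly levels is not given.
- That every AE leading to discontinuation is affected. Only those with no later active dose are.
- That events after completion or an unrelated stop are certainly unaffected. This is not established either way. On weekly epoetin the last active dose can precede the last blinded dose by some days. No figure is put on this class here.
- That the safety comparison as a whole is distorted. The size in any table depends on t and f, both unknown, and is probably small: about 1.4 epoetin participants in the illustration.

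**What to change.** Add post-randomization versions of Tables 3.108 to 3.111 and 3.114, and of the fatal rows of 3.115, beside the treatment-emergent ones. The phase is already defined in section 14.4.1.4 and already used for SAEs and AESIs, so no new data or derivation is needed. State in section 8.3.3 that between-arm differences in the treatment-emergent versions are to be read together with the post-randomization versions, because the window depends on dosing frequency.

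Optionally, add a sensitivity version with the window ending one day after Treatment Stop Date, specified as the last dose of either blinded component. Follow-up and censoring dates would have to match.

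The cost is about five more tables. The post-randomization versions will include events long after study drug stopped, since participants who discontinue are followed to Week 52 and rescued participants are treated by local practice. This can dilute real differences, so these tables should not become the sole between-arm comparison. The optional version would count AEs in a final zero-dose period as treatment emergent and would depart from the active-dose anchor used for laboratory, blood pressure and medication data. The main treatment-emergent definition should be kept.

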9.2.1. Time Period and Frequency for Collecting AE and SAE Information

- All SAEs will be collected from the start of study treatment until the follow-up visit at the time points specified in the SoA (Section 2). However, any SAEs assessed as related to study participation (e.g., study treatment, protocol-

mandated procedures, invasive tests, or change in existing therapy) or related to a GSK product will be recorded from the time a participant consents to participate in the study.

- All AEs will be collected from the start of treatment until the follow-up visit at the time points specified in the SoA (Section 2).
- Medical occurrences that begin before the start of study treatment but after obtaining informed consent will be recorded on the Medical History/Current Medical Conditions section of the case report form (CRF) not the AE section.
- All SAEs will be recorded and reported to the sponsor or designee immediately and under no circumstances should this exceed 24 hours, as indicated in [Appendix 3](#). The investigator will submit any updated SAE data to the sponsor within 24 hours of it being available.
- Investigators are not obligated to actively seek AEs or SAEs in former study participants. However, if the investigator learns of any SAE, including a death, at any time after a participant has been discharged from the study, and he/she considers the event to be reasonably related to the study treatment or study participation, the investigator must promptly notify the sponsor.
- The method of recording, evaluating, and assessing causality of AEs and SAEs and the procedures for completing and transmitting SAE reports are provided in [Appendix 3](#).

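### In the follow-up phase, AE worsening is measured against a pre-treatment intensity that most AEs do not have, so worsening after the last dose is missed or mixed with AEs that did not worsen

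*SAP*

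**What the plan says.** SAP 14.4.1.4 sorts AEs into study phases by onset date or worsening date. An AE falls in the follow-up phase "If AE onset date or AE worsening date is after the last non-zero dose date plus 1 day".

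Each phase has its own reference for worsening:

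- Post-randomization: "AE worsening during post-randomization will be defined relative to the maximum intensity of AE prior to randomization date".
- Treatment emergent: "AE worsening during treatment emergent period will be defined relative to the maximum intensity of AE prior to study treatment start date".
- Follow-up: "AE worsening during follow-up will be defined relative to the maximum intensity of AE prior to study treatment start date".

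The follow-up row then dates the event from the same pre-treatment reference: "AE worsening date is the first date in the follow-up period, when AE intensity increased relative to the maximum intensity of the AE" before treatment start. The introduction to the section adds that "AE of worsening of an on-going event will be counted once in a particular study phase". The notes below the table deal with treatment interruptions and missing dates. They give no on-treatment reference and no rule for an AE that lacks a pre-treatment intensity.

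On data collection, Protocol 9.2.1 says "All AEs will be collected from the start of treatment until the follow-up visit". "Medical occurrences that begin before the start of study treatment but after obtaining informed consent" go to medical history instead. The exception is SAEs related to study participation or to a sponsor product, which are recorded from consent.

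**The concern.** The follow-up phase starts after the last active dose, but its reference for worsening stops at the first dose. Everything the AE did on treatment is left out of the comparison.

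For an AE that began on treatment there is normally nothing to compare with. A programmer has to decide what a missing reference means, and the two obvious choices give opposite tables.

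The row feeds the follow-up summaries of AESIs (Tables 3.062 to 3.070), all AEs (3.091) and SAEs (3.102). The AESI summaries include rates per 100 person-years (SAP 8.3.1). Time at risk for follow-up AEs starts two days after the last non-zero dose and, for a participant with the AE, runs to the event (SAP 14.6.4.3). A wrong flag can therefore add an event and shorten that participant's time at risk.

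Follow-up is not always a short tail. Participants who stop treatment early stay in the study with visits to Week 52 (Protocol 8.1.1), and AEs are collected at those visits (Protocol Table 2). Worsening after stopping is something these tables should show reliably.

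**Working it through.** The plan states no figure to reproduce. This is a classification rule, so the check lists every possible case.

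**Inputs.** Intensity has three levels: mild = 1, moderate = 2, severe = 3 (Protocol 12.3.4). Give each AE one level per phase: P before treatment, T on treatment, F in follow-up.

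**Rules compared.**

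- SAP rule, reading an increase as a level above the reference: flag if F > P.
- Rule on the pattern of the other two rows (worst intensity before the phase starts): flag if F > max(P, T), or F > T when P does not exist.

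**AE began on treatment (P does not exist).** There are 3 × 3 = 9 paths (T, F). True worsening, F > T, occurs in three: (1,2), (1,3) and (2,3).

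- If a missing reference means no flag, the SAP rule flags 0 and misses all 3, including mild on treatment to severe after the last dose.
- If a missing reference is treated as lowest (P = 0), the SAP rule flags all 9. Six are wrong: three unchanged, (1,1), (2,2), (3,3), and three improving, (2,1), (3,1), (3,2).

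**Pre-treatment intensity exists.** There are 3 × 3 × 3 = 27 paths (P, T, F).

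- SAP rule: F > P holds for 3 of the 9 (P, F) pairs, and T is free, so 3 × 3 = 9 flags.
- True worsening: F = 2 needs P = T = 1 (1 path); F = 3 needs P and T both at most 2 (2 × 2 = 4 paths); total 5.
- Wrong flags: 9 − 5 = 4. Three are unchanged from the on-treatment level, (1,2,2), (1,3,3) and (2,3,3). One is improving, (1,3,2).
- Missed: 0, because F > max(P, T) implies F > P.

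| AE type | Paths | True worsening | Flagged by SAP | Missed | Wrongly flagged |
|---|---|---|---|---|---|
| Began on treatment, missing = no flag | 9 | 3 | 0 | 3 | 0 |
| Began on treatment, missing = lowest | 9 | 3 | 9 | 0 | 6 |
| Pre-treatment intensity recorded | 27 | 5 | 9 | 0 | 4 |

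These counts show which errors are possible. They are not frequencies.

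**Which row of the table applies.** Under Protocol 9.2.1 and the matching text in SAP 14.4.1.4, a pre-treatment intensity exists essentially only for a related SAE recorded between consent and first dose. The first two rows are therefore the usual case.

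**The case against.** The best defence has four parts.

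**The follow-up row may be read more carefully than the enumeration reads it.** It dates worsening at the first follow-up date on which intensity *increased*. A move from severe to moderate is not an increase taking place in follow-up. If a programmer also requires a rise dated in that phase, the wrong flags disappear. That is fair, and over-flagging does depend on this reading. But the SAP does not state the extra condition, and the condition does not supply a reference for an AE that began on treatment.

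**A fixed pre-treatment baseline may be deliberate.** The SAP does not say so. If it were, the rule would still be undefined for most AEs.

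**The striking case is rare.** Mild before treatment, severe on it and moderate afterwards needs a related SAE from screening that is still ongoing after the last dose. This stands, and the case carries little weight here.

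**The effect needs an intensity change dated after the last dose.** Protocol 9.2.3 requires follow-up to resolution only for SAEs and non-serious AESIs. This also stands and limits how often the problem can arise.

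A reader might infer that the rule moves events between phases or corrupts the treatment-emergent tables. The documents do not support that. Treatment-emergent and post-randomization status have their own rules, and an AE with onset on treatment stays in both whatever the follow-up row says. Nor is an AE that appears in two phases double-counted by mistake: worsening is counted once per phase, and the phases are summarized separately by design. It would also be too strong to say that every follow-up display turns on this rule, because AEs with onset in follow-up are classified correctly by onset date.

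**Conclusion.** The point holds as a defect in one row of the SAP. The reference for worsening in follow-up breaks the pattern of the other two rows. For AEs that began on treatment it usually does not exist, and the SAP is silent on what to do then. Two programmers could both follow the text and produce different follow-up tables, neither of which isolates true worsening.

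Its reach is limited. Only worsening-based entries, and the rates built on them, change in the descriptive follow-up displays. The treatment-emergent and post-randomization tables and the efficacy analyses do not change. In Table 3.091, which counts participants, an added or omitted worsening matters only if the participant has no other qualifying follow-up event for that term.

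The conclusion that true worsening is missed assumes that a missing reference yields no flag. The conclusion that unchanged or improving AEs are flagged assumes that an increase means a level above the reference and, for AEs that began on treatment, that missing is coded as lowest. The documents do not say how many AEs are ongoing at the boundary or have a later intensity record, so no size in participants or events can be given. The change is worth making before unblinding because it is cheap and removes an arbitrary programming choice.

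**What to change.** In the Follow-up row of SAP 14.4.1.4:

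1. In both sentences, replace the reference with the maximum intensity of the AE on or before last non-zero dose date + 1 day.
2. Define the worsening date as the first follow-up date on which intensity exceeds that maximum.
3. State that an AE with no earlier intensity is classified by its onset date.

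Under this rule the missed and wrongly flagged paths in the enumeration all fall to zero. The cost is two phrases and one added sentence in the SAP, and a small change to the AE derivation. No new data, endpoint, test or display is needed.
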